iIMPACT

INCONTINENCE & INTIMATE PARTNERS: ASSESSING THE CONTRIBUTION OF TREATMENT

[name]
[name] MD, MSME
LOYOLA UNIVERSITY MEDICAL CENTER, MAYWOOD, IL

PROTOCOL DATE: 10/19/2011
REVISED 06/01/2018

INTRODUCTION

Urge urinary incontinence (UUI) is a socially debilitating disease due to its inherently unpredictable nature and sometimes large volumes of urine loss. Women with UUI may experience anxiety over public episodes of incontinence and concerns about odor and as a result, isolate themselves socially. This isolation affects both partners in the relationship and may be a source of discord. The impact of UUI also moves into personal relationships where fears or actual episodes of incontinence during physical intimacy, including but limited to intercourse, may result in limited interactions and changes in the relationship satisfaction for both partners. Few studies have examined the role of urinary incontinence, particularly UUI, in the dynamics of an intimate partner relationship and none have evaluated the impact of successful UUI treatment.

The long-term goal of our research is to understand the social and emotional impact of pelvic floor disorders, particularly UUI, on the well-being of an intimate relationship. Ultimately, we aim to evaluate the role that successful treatment plays in the alleviation of discord in intimate partner relationships that are affected by UUI and other pelvic floor disorders.

Our *objective* for this proposal is to characterize, using validated, quantifiable methods the quality of the relationship in couples affected by UUI and to identify the role that treatment plays in improving this relationship. Our *central hypothesis* is that UUI has a negative impact upon the emotional and physical well-being of a relationship and that effective treatment will result in improvement in areas of the relationship that have been detrimentally affected by UUI. Our *rationale* for this study is that an understanding of UUI in the context of a couple, particularly from the perspective of the male partner, will improve our ability to holistically treat UUI, thus improving patient outcomes and satisfaction.

To test our central hypothesis and complete the objective outlined in this proposal, we propose the following *specific aims*:

Specific Aim #1: To define the levels of relationship satisfaction and sexual function among couples with the female partner having primarily: UUI symptoms and mixed urinary incontinence (urge predominant).

Hypothesis 1: Couples with (female partner) UUI will have lower levels of relationship satisfaction and sexual function based upon validated measures of sexual function and relationship cohesion.

Specific Aim #2: To measure the impact of successful treatment of UUI on the relationship.

Hypothesis 1: Successful treatment with Vesicare will result in improvement in relationship satisfaction and sexual function for both male and female partners.

We expect that the results of this prospective study will allow us to objectively quantify the degree to which intimate relationships are affected by UUI thus filling a critical gap in our knowledge. We also expect to demonstrate that successful treatment of UUI leads to an improvement in relationship satisfaction and sexual function.

Significance of the Proposed Work

Chronic illness places emotional, physical, and financial burdens upon both the patient and her partner, and can be a significant source of stress in a relationship. The symptoms of UUI inherently pose greater social challenges than those faced by women with other forms of pelvic floor disorders. For example, women with UUI may avoid social situations due to fear of having an accident or may be reluctant to participate in activities during which it may be difficult to find a bathroom. The resulting social isolation impacts both members of the dyad and may serve as a source of relationship discord. Changes in sexual function and perceived intimacy, including non-intercourse intimacy, as well as communication may be new sources of stress in a previously healthy relationship or may serve to amplify pre-existing relationship problems.

Sexual function is another area in which UUI may cause a negative impact. Studies of coital incontinence among incontinent clinic populations report prevalence ranging from 10%-56% with a median of 22% (1). The prevalence of coital incontinence may be related to the type of incontinence as well as the severity of symptoms. Stress incontinence has been associated with leakage of urine during intercourse, while detrusor instability and urge incontinence have been correlated with leakage during orgasm (2). A cross-sectional study of women with UUI and urinary incontinence found that among women reporting low sexual desire, stress incontinence was common (47%), while 46% of women reporting orgasmic phase dysfunction reported symptoms of urge incontinence (3). Qualitative data corroborates the negative impact of UUI on dyadic and sexual relations (4).

Another mechanism by which UUI may affect satisfaction with dyadic relations is through depressive symptomatology. Urinary incontinence is associated with a decrease in overall health-related quality of life and is positively correlated with depression, anxiety, and stress (5-7). Studies of other chronic illnesses demonstrate a correlation between the patient's level of depression and that of their spouse; level of depression shows an inverse relationship with degree of satisfaction with the relationship (8).

One of the two studies in the published literature that use quantitative methods to evaluate the impact of urodynamic stress incontinence and detrusor overactivity on the marital relationship concluded that both sexual function and marital relationships are negatively affected by incontinence (9). This study, like others, is based upon the perspective of the female partner. A recent study of Swedish women with urinary incontinence and urgency is the only study which includes the perspective of the male partner to examine the impact of UUI on the relationship (10). It concludes that, "Female urinary incontinence, urgency and frequency significantly impair the quality of life in both younger and older women, and also have negative effects on the partner relationship and the partner's life".

The perspective of intimate partners of women with UUI and other forms of PFD is largely missing from the literature. Any analysis of the role of UUI in intimate partner relationships is incomplete without this perspective.

Methodology

All women presenting with a chief complaint of UUI or MUI urge predominant with three months of symptoms presenting to the Division of Female Pelvic Medicine & Reconstructive Surgery at Loyola University Medical Center who meet the inclusion criteria will be invited to participate in this prospective study.

For the purposes of the study, women with UUI predominance will be defined as those women with an urge symptom index of $\geq 50\%$ on the MESA who are not planning to undergo surgical correction of pelvic organ prolapse or stress urinary incontinence.

Following informed consent the following information will be extracted from their medical records (all obtained as part of routine gynecologic care):

- Demographics: age, self-reported race and ethnicity, vaginal parity, marital status, years with current partner, BMI, menopausal and hormone replacement status, prior treatment for pelvic floor disorders, prior medical and surgical history
- The Pelvic Floor Distress Inventory-Short Form 20 (PFDI-20) (11), a validated, condition-specific pelvic symptom questionnaire
- The Medical, Epidemiological, and Social Aspects of Aging (MESA) (12)
- The patient's goals for her treatment

As part of the study, women enrolled in this study will complete the following validated questionnaires:

- The Pelvic Organ Prolapse/Urinary Incontinence Sexual Function Questionnaire (PISQ-12) (13) and the Pelvic Floor Impact Questionnaire-Short Form 7 (PFIQ-7) (11), validated questionnaires measuring the impact of pelvic floor dysfunction, including urinary incontinence, on sexual function and general quality of life, respectively.
- The Golombok-Rust Inventory of Sexual Satisfaction (GRISS) (14).
- The Dyadic Adjustment Scale (DAS) (15).

Consenting male partners of women enrolled in this study will complete a questionnaire that includes information on:

- Demographics: age, BMI, and general health status.
- The Golombok-Rust Inventory of Sexual Satisfaction (GRISS)
- The Dyadic Adjustment Scale (DAS)

- Their goals for their partner's treatment

The Golombok-Rust Inventory of Sexual Satisfaction (GRISS) is a 28-item self-administered questionnaire that was developed by sex therapists to assess the quality of the sexual relationship of a heterosexual couple. The survey, which takes approximately 15 minutes to complete, evaluates 12 domains, 5 of which are female-specific, 5 male-specific, and 2 non-gender specific. The GRISS receives a Grade A recommendation from the International Continence Society for its appropriateness as a tool for evaluating sexual function as a dimension of overall health-related quality of life among patients with pelvic floor disorders.

The female version produces a Total GRISS Female Score as well as subscales of:

- *Anorgasmia* - the extent to which a woman is able to attain orgasm.
- *Vaginismus* - the extent of any tightness around the vagina that interferes with sex.
- *Non-communication* - The extent to which a couple are able to talk about any sexual problems.
- *Infrequency* - The number of times a week (or less) on which sexual intercourse takes place.
- *Female Avoidance* - The extent to which a female partner is actively avoiding having sex.
- *Female Non-sensuality* - The extent to which a female partner gains pleasure from touching and caressing.
- *Female Dissatisfaction* - The extent to which a woman is dissatisfied with their sexual partner.

The male version produces a Total GRISS Male Score as well as subscales of:

- *Impotence* - the extent of any failure by a man to achieve an erection.
- *Premature ejaculation* - the extent to which a man has the tendency to ejaculate too soon.
- *Male Avoidance* - The extent to which a male partner is actively avoiding having sex.
- *Male Non-sensuality* - The extent to which a male partner gains pleasure from touching and caressing.
- *Male Dissatisfaction* - The extent to which a man is dissatisfied with their sexual partner.
- *Non-communication & Infrequency* – Same as the female version

The Dyadic Adjustment Score is a validated instrument for evaluation of adjustment in relationships between either married or unmarried cohabiting couples. It may be used at baseline to obtain a comprehensive description of the relationship and as an objective measure of change in the interaction between partners after an intervention. The DAS consists of a 32-item self-administered questionnaire that is not gender specific. It has four subscales: relationship satisfaction, cohesion, consensus, and affectional expression. The DAS takes 5-10 minutes to complete.

All women presenting with a chief complaint of 3 months of UUI or mixed urinary incontinence (MUI) with urge predominance to the Division of Female Pelvic Medicine & Reconstructive Surgery at Loyola University Medical Center who meet inclusion criteria will be approached for study participation. Women will receive a thorough explanation of the study, including the risks, benefits, and potential side effects of the study drug, and their questions will be answered. Women of childbearing age will be counseled that they should be using an effective method of birth control during the study. They will sign an informed consent document. They will also be given a 3 day voiding diary to be completed at home. Prior to completing the 3 day voiding diary, patients currently taking an anticholinergic medication will undergo a 2 week wash out period during which

they will not take any drug. They will also be given a letter describing the study to give to their partner.

Women with a diagnosis of UUI or MUI, urge predominant, who have consented to participate and whose partners consent to participate will return to the clinic with completed study questionnaires (PISQ-12, PFIQ-7, MESA, GRISS, and DAS).

They will be given Vesicare 5mg with instructions for use. After 4 weeks of use, we anticipate that 50% of patients will note improvement. Those who do not feel that their symptoms are adequately controlled will have the option of increasing to 10 mg per day for the remaining 8 weeks of the study. After 12 weeks of medication use, patients will have a follow up visit, they will be asked to again complete all of the PISQ-12, PFIQ-7, MESA, GRISS, and DAS as well as the Overall Quality of Life Related to Urinary Incontinence Questionnaire. Male partners will also complete a second set of questionnaires either in the clinic or at home after their partner has undergone 12 weeks of treatment. Patients will be given a total of 16 weeks of Vesicare to allow for some variation in scheduling follow up and to ensure that they are currently taking Vesicare at the time that they complete their follow up questionnaires.

Subjects and Recruitment

Loyola's clinical research team is well-suited to successfully recruit women to this study. Our division has four clinical faculty members, all of whom are NIH funded investigators who participate in large clinical and surgical trials through the Urinary Incontinence Treatment Network and the Pelvic Floor Disorders Network. In addition, we have 4 full-time research nurses and a data entry manager. The entire group is fully supportive of this research.

Recruitment of men for studies on female urinary incontinence is a new area of research. This study would be the first to exam relationship dynamics from the perspective of the male partner using validated methods. Based upon a small pilot study of male partners that was conducted at our center, we believe that the recruitment of male partners is a feasible goal. Because there is no direct benefit to the male partner and given the personal nature of the data collected, compensation of the male partners (travel and parking) is reasonable and likely to give a more representative sample.

Subjects will be recruited from all racial and ethnic groups. Race and ethnicity will be determined by self-reporting according to the guidelines of The Office of Management and Budget Directive No. 15. On the screening questionnaire, subjects will be allowed to choose from 2 ethnic categories, "Hispanic or Latina" and "Not Hispanic or Latina". They will also choose from 5 racial categories: American Indian or Alaska Native; Asian; Black or African American; Native Hawaiian or Other Pacific Islander; and White. Appropriate definitions will be included on the questionnaire.

Women will eligible for *inclusion* in the study if they are:

- Age \geq 18 years, and
- In a relationship with a male partner for at least 3 months, and
- Not pregnant (pregnancy test will be done at study enrollment) or planning to become pregnant, and

- Have a diagnosis of UUI or MUI, urge predominant, based on recall
- Are interested in medical management of their symptoms and are candidates for Vesicare, and
- Able to provide informed consent and complete the written questionnaires.

Women will **excluded** from participation in the study if they have:

- PVR > 200 ml at initial visit
- Significant outflow obstruction
- Persistent/recurrent UTI
- Bladder stones
- A diagnosis of chronic interstitial cystitis
- Undergone pelvic irradiation
- Current pelvic malignancy
- Narrow angle glaucoma
- Urinary or gastric retention
- Current use of a tricyclic antidepressant
- A neurologic diagnosis that could affect bladder function (MS)
- A diagnosis of chronic pelvic pain
- An active psychotic disorder

Women will also be **ineligible** for participation if they:

- Or their partner is non-English speaking
- Decline permission for the study team to approach their partner regarding participation

Statistical Analysis

Power Analysis

While the change in the overall GRISS score is the primary outcome in this study, the sample size for this study is based upon published research utilizing the DAS (i.e., which also measures relationship satisfaction).

A prior study of the relative effectiveness of two behavioral interventions in the treatment of marital discord randomized 45 couples to a known intervention, an experimental intervention, or a wait list (control group)(16). This sample size was adequate to demonstrate a significant change in DAS score in response to the study intervention. Similarly, a study of 36 couples detected significant changes in DAS scores following an intervention that consisted of several variants of marital therapy (17). Similar sample sizes have been used in the published literature of studies using the DAS as an indicator of improvement in marital quality (18, 19). This study will recruit 100 couples (200 subjects) with the assumption of a 50% response rate to the study drug (Vesicare). This will allow for a final sample size of 40-50 couples, consistent with that of other studies in the published literature.

Statistical Analysis Plan

In this study, the Global Impression of Improvement (GII) score is used to indicate response to therapy following three months of treatment, where response to treatment comprises those who rate their Global Impression of Improvement (GII) as "a little better", "much better", or "very much better". Conversely, non-response to treatment comprises those who rate their GII as "no change", "a little worse", "much worse", or "very much worse".

Participants' baseline characteristics will be stratified by sex and compared between responders and non-responders using Pearson chi-square tests. For females, this includes comparisons between responders and non-responders on age (i.e., ≥ 60 versus < 60), race, marital status, education attainment, years living with a partner (i.e., ≥ 30 versus < 30), body mass index (i.e., ≥ 30 versus < 30 kg/m²), menstrual cycle, vaginal parity, prior treatment for pelvic floor disorders, prior surgery, and prior treatment for overactive bladder treatment. For males, this includes comparisons between responders and non-responders on age (as specified above), current sexual activity, general health, and medical history of hypertension, erectile dysfunction, arthritis, diabetes, cancer, heart disease, and depression. For these baseline comparisons, expected frequencies will be monitored and Fisher's exact tests will be used when such values are sparse.

For Aim 1, baseline Golombok Rust Inventory of Sexual Satisfaction (GRISS) scores will be compared between matched male and female partners using a paired samples *t*-test. The difference between female and male responses will be assessed for normality using a QQ plot and for outliers using a boxplot. If parametric assumptions are violated, conclusions may be confirmed using a Wilcoxon signed-rank test.

For Aim 2 we will subtract participants' overall 3-month GRISS score from their overall baseline score and compare this change in GRISS between those who respond and do not respond to solifenacin using an independent samples *t*-test. As before, the normal distribution of the change score in each response group will be assessed graphically using a QQ plot and for outliers using a box-plot. If parametric assumptions are violated, conclusions may be confirmed using a non-parametric Wilcoxon rank-sum test.

Finally, healthy male partners of female participants also complete the GRISS at baseline and after their female partner completes approximately 12-16 weeks of solifenacin treatment for UUI symptoms. For these male partners, a change score will be calculated by subtracting their baseline score from the follow-up score. This change score will be compared between male partners of female participants who respond to solifenacin versus male partners of female participants who do not respond to solifenacin.

All statistical analysis will be conducted using SAS Version 9.4 (SAS Institutes, Cary, NC) with the input of a Biostatistician.

References

1. Shaw C. A systematic review of the literature on the prevalence of sexual impairment in women with urinary incontinence and the prevalence of urinary leakage during sexual activity. *Eur Urol*. 2002 Nov;42(5):432-40.
2. Hilton P. Urinary incontinence during sexual intercourse: A common, but rarely volunteered, symptom. *Br J Obstet Gynaecol*. 1988 Apr;95(4):377-81.

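### The Aim 2 responder comparison is unadjusted, and its baseline check omits incontinence type and severity, so an imbalance in either could contribute to the GRISS-change difference unseen

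*Combined protocol and SAP*

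**What the plan says.** All references are to the combined protocol and SAP.

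- **Population.** Specific Aim #1 concerns couples with the "female partner having primarily: UUI symptoms and mixed urinary incontinence (urge predominant"). The inclusion criteria under Subjects and Recruitment accept either type: "Have a diagnosis of UUI or MUI, urge predominant, based on recall". Methodology gives one operational definition: "women with UUI predominance will be defined as those women with an urge symptom index of" at least 50% on the MESA. Women planning surgery for prolapse or stress incontinence fall outside it. No rule separates UUI from mixed incontinence (MUI).
- **Rationale.** Significance of the Proposed Work states: "The prevalence of coital incontinence may be related to the type of incontinence as well as the severity of symptoms". It adds: "Stress incontinence has been associated with leakage of urine during intercourse, while detrusor instability and urge incontinence have been correlated with leakage during orgasm".
- **Baseline check.** The Statistical Analysis Plan compares response groups at baseline: "For females, this includes comparisons between responders and non-responders on age", followed by ten further items.
- **Aim 2.** GRISS change is compared by response (any improvement on the GII) with an independent-samples t-test. Male partners are compared on the same split after the woman "completes approximately 12-16 weeks of solifenacin treatment for UUI symptoms". Neither comparison has a covariate.
- **MESA.** Methodology has it completed at baseline and again after 12 weeks. No analysis uses it.

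**The concern.** Women sort themselves into response groups by their own global rating, so the groups can differ at baseline in ways that also affect how far GRISS moves. Incontinence type is a natural candidate. Treatment is described as directed at UUI symptoms, whereas the GII is not specific to urge symptoms. A woman with a marked stress component might rate her improvement lower and also have less room for sexual function to improve. Type is fixed before both.

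On that pathway responders would look better than non-responders even if response itself did nothing, which is the direction the Aim 2 hypothesis predicts. Baseline severity could act in a similar way, in either direction. The planned baseline table is the only place where an imbalance could come to light, and it contains neither variable.

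**Working it through.** **1. Count of the female baseline list (Statistical Analysis Plan).** Age, race, marital status, education, years living with a partner, BMI, menstrual status, vaginal parity, earlier pelvic floor treatment, earlier surgery and earlier overactive-bladder treatment: 11 items. None is incontinence type, MESA or another severity score.

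**2. The plan's own numbers (Power Analysis).** 100 couples × 0.50 response = 50, the upper end of the stated 40-50. The lower end, 40, needs a further loss of 1 − 40/50 = 20%, which is not stated. No alpha, SD or effect size is given. Below, 50 per group stands for all 100 couples followed with half responding, and 25 per group for a final total of 50. A two-sided 5% test is assumed.

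**3. Possible distortion of Aim 2.** The documents give no MUI share and no effect of type on GRISS change, so all inputs here are assumptions. Let q0 and q1 be the MUI share in non-responders and responders, g the shortfall in GRISS change in MUI couples (in within-type SDs), and let response itself have no effect.

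- Spurious difference = (q0 − q1) × g
- SE = √{[1 + q0(1 − q0)g²]/n + [1 + q1(1 − q1)g²]/n}
- False-positive rate = Φ(diff/SE − 1.96) + Φ(−diff/SE − 1.96)

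| q0, q1 | g | Spurious difference | False-positive rate, n = 25 per group | n = 50 per group |
|---|---|---|---|---|
| equal | any | 0 | 5% | 5% |
| any | 0 | 0 | 5% | 5% |
| 0.55, 0.45 | 0.3 | 0.10 × 0.3 = 0.03 SD | 5.1% | 5.3% |
| 0.60, 0.40 | 0.5 | 0.20 × 0.5 = 0.10 SD | 6.4% | 7.7% |
| 0.60, 0.30 | 0.5 | 0.30 × 0.5 = 0.15 SD | 8.1% | 11.3% |
| 0.70, 0.30 | 0.7 | 0.40 × 0.7 = 0.28 SD | 15.6% | 26.6% |

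For the 0.15 SD row, SE = √[(1.060 + 1.0525)/50] = 0.206 SD at 50 per group, or 0.291 SD at 25. The distortion is then less than one standard error.

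**4. Cost of adjusting for type.** With equal response groups and an overall MUI share of one half, the correlation r between type and response equals the gap in MUI share, and variance inflation is 1/(1 − r²). Gaps of 10, 20 and 40 points give 1.01, 1.04 and 1.19. Even the last widens the interval by only √1.19 − 1 = 9%.

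**5. Precision of Aim 1 by type.** The 95% half-width for a mean female-male difference is t/√n, in SDs of that difference.

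- 100 couples pooled: 1.984/10 = 0.20 SD
- 100 couples split evenly: 2.010/√50 = 0.28 SD per type
- 50 couples split evenly: 2.064/√25 = 0.41 SD per type
- A type with 15 couples: 2.145/√15 = 0.55 SD

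For 80% power, a UUI-MUI contrast in 100 couples needs (1.960 + 0.842) × √(1/50 + 1/50) = 0.56 SD at an even split, or 0.61 SD at 30/70.

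**The case against.** The case against is substantial, and much of it stands.

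- **Change scores.** A stress-leakage effect that is the same at both visits cancels in GRISS change. This is correct. What remains is a difference in how much couples can improve, which a change score does not remove.
- **Mechanism.** If women with UUI improve more because their urge leakage was treated, that is largely the effect Aim 2 seeks. This also stands in part, and it is why any adjustment should use baseline MESA only, not the 12-week value.
- **Weak link to response.** The lowest grade of improvement on the GII counts as response, women planning stress-incontinence surgery are outside the definition, and the rationale concerns leakage by type, not response to treatment. These facts make a large imbalance less likely. They do not rule one out.
- **One factor among many.** No covariate at all is used in Aim 2. True, but type and severity are the ones the protocol itself connects with sexual leakage, and the MESA is already in hand.

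A reader might go further and infer that Aim 1 is answered for neither population it names. The documents do not support that. The sentence reads at least equally well as describing one urge-predominant group: there is a single MESA definition, either diagnosis qualifies, and the hypothesis speaks of one group, "Couples with (female partner) UUI will have lower levels of relationship satisfaction and sexual function". No contrast between UUI and MUI is proposed. On that reading a pooled result matches the population.

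**Conclusion.** The gap is real but modest. Aim 2 is an unadjusted, non-randomised contrast, and neither it nor its baseline table uses incontinence type or baseline severity. A contribution from either could go unnoticed. A reader might also infer that Aim 2 is shown to be confounded by stress leakage; it is not. Distortion requires type or severity to be related both to the GII rating and to GRISS change, and the documents give no figure for either link.

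The size is unknown. It is zero if either link is absent, and about 0.03 to 0.28 SD if the MUI share differs by 10 to 40 points and GRISS change differs by 0.3 to 0.7 SD between types. All of these inputs are assumed. The case for acting rests on the low cost of the check, not on a demonstrated bias.

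**What to change.** 1. **Baseline table.** Add the baseline MESA urge index, and UUI versus urge-predominant MUI, to the female responder comparison. Fix the definition of type before analysis. The documents name no MESA stress score and base diagnosis on recall, so this definition has to be written. Because entry requires an index of at least 50%, the index alone may say little about the stress component, which is why type is needed as well.
2. **Sensitivity analysis for Aim 2.** For women and for male partners, regress GRISS change on response, adjusted for the woman's baseline MESA urge index and type. Report this beside the unadjusted estimate with confidence intervals, and state in advance that a material shift in the estimate limits the Aim 2 conclusion, with what counts as material written down.
3. **Aim 1.** State that it is pooled over urge-predominant women, and give baseline GRISS by type descriptively with confidence intervals. Plan no powered UUI-MUI test.

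The cost is SAP wording, a few table rows and one extra model for each partner. No new questionnaire is needed. The downsides are slightly wider intervals in the adjusted model (1 to 19% more variance from type for gaps of 10 to 40 points, plus a little for the urge index) and imprecise by-type estimates: about ±0.28 SD per type with 100 couples split evenly, and ±0.41 SD with 50.

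### Aim 2 is worded as a causal effect of successful Vesicare treatment, but its planned contrast can show only an association with self-rated improvement

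*Combined protocol and SAP*

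**What the plan says.** The causal wording appears in three places.

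- Specific Aim #2, Hypothesis 1: "Successful treatment with Vesicare will result in improvement in relationship satisfaction and sexual function for both male and female partners".
- The expected-results paragraph after the aims: "We also expect to demonstrate that successful treatment of UUI leads to an improvement in relationship satisfaction and sexual function".
- The central hypothesis in the Introduction, which predicts that effective treatment will bring improvement in the parts of the relationship that UUI has harmed.

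On treatment, the Methodology section says of the consenting women: "They will be given Vesicare 5mg with instructions for use". No placebo, untreated, wait-list or randomised group is described anywhere.

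The Statistical Analysis Plan forms the groups from the woman's own Global Impression of Improvement (GII) after three months. Any grade of improvement, including the smallest, counts as response. For Aim 2 it will "compare this change in GRISS between those who respond and do not respond to solifenacin using an independent samples" t-test. For the men, it compares change in "male partners of female participants who respond to solifenacin versus male partners of female participants who do not respond to solifenacin". The Power Analysis section names change in overall GRISS as the primary outcome.

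Neither contrast is adjusted for covariates. Baseline characteristics are only tabulated and tested by response group. No passage limits the causal reading of the result.

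**The concern.** Both groups take the study drug, and they are sorted after baseline by how the woman feels. The contrast therefore does not compare taking Vesicare with not taking it. It compares women on Vesicare who feel better with women on Vesicare who do not.

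Many things besides the drug can put a woman in the improved group: fluctuating symptoms, having presented at a bad time, expectation, or events that ease both the bladder and the relationship. The direction is open as well, because a better relationship can raise a global rating. The Significance section itself links incontinence with depression, and depression with lower relationship satisfaction. Yet the planned baseline comparisons list depression for men only.

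At stake is what may be concluded on the declared primary outcome. Under the present wording, a significant difference would naturally be reported as a benefit to couples from successful Vesicare treatment. The data would show only that GRISS changed more in couples where the woman reported improvement.

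**Working it through.** **The plan's own figure.** The Power Analysis section recruits 100 couples, assumes 50% response and arrives at 40-50 couples. 100 × 0.50 = 50 gives the upper end. The lower end needs a further loss of 1 − 40/50 = 20%, which is not stated. No effect size, SD, alpha or power is given, so there is no power calculation to reproduce. It is also unclear whether 40-50 counts responders only or all couples analysed. The illustration below therefore uses both 100 couples (all recruited) and 45 (the middle of 40-50).

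**What the contrast contains.** Write the expected difference in GRISS change between the two groups as D + N. D is the between-group difference in change caused by the drug. N is the between-group difference in change from everything else. The planned t-test estimates the sum, and nothing in the design separates the parts.

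**Case 1: no drug effect, so D = 0.** All of the following are assumptions: standardised GRISS change, a normal latent symptom rating split evenly into improved and not improved, a correlation ρ between the two from non-drug causes, and two-sided alpha 0.05. The expected difference is

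2 × ρ × φ(0)/0.5 = 2 × ρ × 0.798.

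For ρ = 0.30 this is 2 × 0.30 × 0.798 = 0.48 SD.

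Check by formula at ρ = 0.30:
- Within-group variance is 1 − ρ² × 2/π = 1 − 0.09 × 0.637 = 0.943, so the SD is 0.97.
- With 50 women per group, the standard error is 0.97 × √(2/50) = 0.194.
- The noncentrality is 0.479/0.194 ≈ 2.47, which gives about 68% rejection.

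Simulating the women's t-test (4,000 trials per cell, zero drug effect) gives:

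| Assumed ρ | Expected difference (SD) | Significant, 100 couples | Significant, 45 couples |
|---|---|---|---|
| 0 | 0 | about 5% | about 5% |
| 0.2 | 0.32 | about 35% | about 17% |
| 0.3 | 0.48 | about 67% | about 36% |
| 0.5 | 0.80 | about 99% | about 81% |

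**Case 2: a real benefit shared equally by all women.** If every woman gains c, both group means rise by c and the expected difference is c − c = 0. With c = 0.5 SD, no non-drug correlation and 100 couples, the simulated mean difference was 0.003 SD and the test was significant in 5.5% of trials, which is close to alpha.

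The contrast can thus be positive with no drug effect, and null with a real one.

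**The case against.** The strongest reply is that the hypothesis is about *successful* treatment. The aim reads "Specific Aim #2: To measure the impact of successful treatment of UUI on the relationship", and the expected-results sentence does not name the drug. On that reading the question is whether symptom relief goes with relationship change, and comparing responders with non-responders addresses it. This stands in part: the contrast is a sensible one for an association. It does not rescue the causal verbs. Success is the woman's own rating after baseline, the hypothesis and the group labels credit it to the drug, and even the effect of symptom relief alone is confounded and of open direction.

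Four stronger readings are tempting, and the documents do not support them.

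- *The trial plans to conclude that Vesicare beats no treatment.* The documents contain a hypothesis and an expectation about successful treatment. No comparison of drug with no drug is stated as a target, and what the report will say is a prediction.
- *The contrast holds no information on the drug.* That is exact only for an effect that is the same in every woman. The protocol supposes that benefit comes through symptom relief. If so, drug benefit does enter the contrast, mixed with the rest. The supportable statement is that the two cannot be separated.
- *The trial has a false-positive rate of some 67%.* That figure belongs to one assumed correlation at 100 couples, and the table shows how far the assumption decides the answer. It covers women only. For the men, one person supplies the GII and another the GRISS, so shared reporting does not act in the same way, and no figure is offered.
- *The protocol's own precedent shows that a control was needed.* The wait-list study in the Power Analysis section is cited for sample size only and is not evidence on attribution.

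It is also fair to say that response to solifenacin is defined operationally through the GII, so relabelling the groups clarifies the text without changing the analysis.

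**Conclusion.** The point holds as a limit on attribution. With all women on Vesicare and groups formed by self-rating at three months, the Aim 2 contrast supports a statement of association. It does not support the causal wording of Hypothesis 1, the expected-results sentence or the central hypothesis.

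That conclusion rests on the design as written and on no numerical assumption. The size of the problem does rest on assumptions. With zero drug effect, the chance of a significant result in women runs from about 5% to 99% at 100 couples, and from about 5% to 81% at 45, as the assumed non-drug correlation goes from 0 to 0.5. The documents give no value for that correlation.

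Because the wording governs what may be concluded on the primary outcome, it should be corrected before the results are reported. A reader might infer that the study must add a control arm. That would follow only if the effect of the drug itself were the aim, and the documents do not say so.

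**What to change.** 1. Restate Aim 2, Hypothesis 1 and the expected-results sentence along these lines, and align the central hypothesis in the Introduction: *Self-rated improvement in UUI symptoms during 12 weeks of open-label Vesicare is associated with greater improvement in GRISS in women and in their male partners.* The sentence is confined to GRISS because the Statistical Analysis Plan gives no Aim 2 test for the DAS.
2. In the Aim 2 and male-partner paragraphs of the Statistical Analysis Plan, describe the groups as women who do or do not report improvement while taking solifenacin, and as the partners of those women.
3. Add a sentence stating that the design does not estimate the effect of Vesicare, and that the report will make no causal or drug-specific claim.

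These are changes of wording only, with no new arm, visit, data or test. The cost is a less favourable headline claim. The change does not remove the confounding; it stops the report from claiming more than the contrast can show.
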